### 3. OVERVIEW OF STUDY DESIGN

The design of the study is illustrated in Figure 1 below. In this prospective randomized pilot study, 10 eligible high-risk subjects with ICAS will be randomized to RLIC (bilateral upper extremity (BUE) daily for 30 days) plus AMM (n=5) or AMM alone (n=5). The AMM, which will be started at study enrollment and continued until close-out in all subjects, will consist of aspirin 325 mg per day, clopidogrel 75 mg per day, and risk factor management primarily targeting a systolic BP < 140 mmHg and LDL cholesterol < 70 mg /dl. All subjects will undergo baseline brain arterial spin labeling (ASL) and perfusion MRI to measure CBF and have blood drawn for biomarkers 3-5 days after randomization to allow for washout of any effect from the test RLIC treatment that will be done prior to randomization to determine the subjects' tolerability to RLIC treatment (see section 5 for more details on screening test). The period of 3-5 days will provide flexibility for scheduling these tests. After the baseline MRI and biomarker tests are completed, the subjects randomized to RLIC will begin daily RLIC for 30 days. Each daily BUE RLIC treatment will consist of 4 cycles of 5-minute inflations of both blood pressure cuffs simultaneously to a pressure of 200 mm Hg with 5 minutes of reperfusion between each inflation using the Doctormate device (see Figure 2). All subjects will return for their close-out visits 33-35 days after enrolling in the study and will undergo brain ASL and perfusion MRI and have blood drawn for biomarkers at that visit. The study will be conducted at 4 sites (MUSC, MCG, UCLA, USC) to enable us to evaluate the consistency of CBF measurements across multiple sites and to ensure that the recruitment target of 10 subjects will be met in time to allow for the subsequent NIH grant submission in 2017.

Figure 1. Overview of Study Design

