## 8. BLOOD BIOMARKER MEASUREMENTS

The blood biomarkers that will be measured are putative biomarkers of RLIC and known inflammatory and fibrinolytic markers associated with the development or progression of ICAS, or increased risk of stroke in patients with ICAS. These consist of: Nitrite, IL-10, SDF1, Micro RNA 144, Lp-PLA2, IL-6, hsCRP, Soluble E-selectin, ICAM, MMP-9, PAI-1, tPA, and ADMA. We will measure the blood biomarkers at baseline and close-out (33-35 days after enrollment) in all 10 subjects. All blood biomarkers will be mailed to the Blood Biomarker Core at MCG where the levels of biomarkers will be measured blinded to site, subject, treatment assignment and time point.

**Figure 2.** The RLIC device used in the Chinese trials will be used in this pilot study and is shown being applied to [name], a Co-PI of this pilot study at Georgia Regents University (center)

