## **9. MRI MEASUREMENTS OF CBF AND OTHER PERfusion PARAMETERS**

ASL MRI will be used to provide quantitative measurements of CBF in all 10 subjects in the study (at baseline and at close-out). ASL does not require the injection of contrast material and can be repeated over time without risk to patients. **We will use a standardized ASL protocol agreed upon by the study radiologists and physicists at the 4 participating sites that can be applied to different MRI scanner platforms.** Each subject will undergo all MR studies for this pilot on the same scanner to limit slight variations in images from scanner to scanner. We have already tested the feasibility of using our planned ASL MRI protocol under a MCG / UCLA IRB-approved protocol. Six subjects with recent stroke from ICAS underwent ASL MRI before and after one RLIC treatment, a mean of 4.6 hours apart. The de-identified scans were sent to UCLA where [name] performed CBF analyses and readings blinded to pre- and post-RLIC treatment. After just 1 cycle of RLIC, these subjects showed mean increases of CBF of 8%-28% in the MCA and PCA territories on the infarct side vs. the normal side. While quantitative CBF obtained with ASL MRI is the primary MR outcome in this pilot, we will also utilize dynamic susceptibility contrast enhanced perfusion MR imaging (DSC-PWI) to assess the effectiveness of secondary brain perfusion parameters (such as cerebral blood volume and cerebrovascular transit times).

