## **10. ASSESSMENT OF FEASIBILITY, TOLERABILITY AND ADHERENCE TO RLIC**

Enrolled subjects randomized to the RLIC group will take the Doctormate device home and use it daily for the next 30 days. The research coordinator will call the subject weekly up until the close-out visit to document any problems with the device or any adverse events using a questionnaire (see Appendix 1). The subject will also be asked to keep a daily diary for the 30 days the Doctormate device is used (see appendix 2.) The device records when it is used and whether the treatment was completed so when the subject returns for the close-out visit, we will be able to assess adherence to use of the device.

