## **11. RANDOMIZATION, BLINDING, AND DATA MANAGEMENT**

Subjects will be randomized 1:1 using a pre-generated exact central randomization list that controls for moderate imbalances at the site level. All study data will be entered directly by either the study PI or stroke coordinator at each site in the RedCap data management system developed at MUSC for the study. Initial data checking will be performed by the system before the data can be saved to prevent low level data errors. When the data are transferred to the study biostatistician for analysis and report generation, further data quality checks will be conducted by SAS. Study data will be retained on a secure server at the Department of Public Health Sciences at MUSC.

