## **12. STATISTICAL ANALYSES**

To estimate the variability in CBF and biomarkers, all of which are continuous measures, simple summary statistics will be reported for the baseline and close-out measurements in each group. With five imaging samples per group, the precision of the 90% confidence interval around the mean would be  $\pm 0.95$  for a SD of 1, and, as an example, would increase to  $\pm 7.63$  for a SD of 8. We will also evaluate the changes in CBF and biomarkers from baseline to close-out in the two groups using means and 90% confidence intervals. Here, the precision of the resulting confidence interval is  $\pm 9.4$  when the SD is 8; that is, if RLIC yields a mean 10% change in CBF and sham RLIC yields a mean 0% change in CBF the resulting 90% confidence interval is (0.6, 19.4) for the difference in percent change in CBF. Finally, with a sample size of N=5, we will be able to estimate the correlation between CBF and biomarkers for each arm with an 90% confidence interval of 0.5 (-0.5, 0.9) in the case of an observed moderate correlation. Interpretation of the summary statistics will be complimented with graphical approaches including boxplots to assess distributions within treatment arms, and funnel plots to assess differences at the site level.

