### **Protection Against Risk**

The research coordinator will call subjects randomized to the RLIC group weekly and will use a standardized questionnaire to ask subjects about adverse events (see Appendix 1). For the pain question, we will utilize a visual analog pain scale of 0 to 10 and provide this to the subjects randomized to the RLIC group. At the weekly phone call, the research coordinator will ask the degree of pain using this scale. If the score is > 2, the site investigator will be notified and will contact the subject by phone to review the level of discomfort. Additionally, If the subject answers "yes" to any other questions, we will ask the subject to come in to be examined. If we suspect a venous thrombosis because of swelling or pain, we will perform a venous ultrasound to rule out a deep venous thrombosis. We will also obtain the phone number of a relative or friend in order to reach the subject if we have trouble reaching the subject. All subjects will be given the telephone numbers of the principal site neurologist and site coordinator to report any clinical events or to ask questions about the study.

Subjects who are claustrophobic will not be enrolled in this study. To reduce the risk of phlebotomy, only trained phlebotomists will perform venipuncture. All neuroimaging and biomarker data will be de-identified as stated under "Sources of Material". Copies of the source documents used to collect data for study subjects will be kept in confidential binders at the participating sites. All these measures will ensure against loss of confidentiality.

Side effects of any medications prescribed to subjects as part of routine care of subjects with intracranial stenosis will also be monitored. These side effects will be minimized by recommending use of enteric-coated aspirin, checking liver enzymes and CK for subjects on a statin if clinically indicated, and instituting appropriate treatment should side effects arise.

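### Does the reference to a sham arm in Section 12, with no stated blinding for reading CBF, undermine the comparison of CBF change?

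*Combined protocol and SAP*

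**What the plan says.** Section 3 randomizes ten subjects to RLIC "plus AMM (n=5) or AMM alone (n=5"). Section 10 gives the device to one arm only: "Enrolled subjects randomized to the RLIC group will take the Doctormate device home and use it daily for the next 30 days". Section 12 then illustrates the comparison with "if RLIC yields a mean 10% change in CBF and sham RLIC yields a mean 0% change in CBF" and reports a 90% interval of (0.6, 19.4) at an SD of 8. The word sham occurs nowhere else in the available text.

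On outcome reading, Section 8 says of the assays that "the levels of biomarkers will be measured blinded to site, subject, treatment assignment and time point". Section 9 says that "quantitative CBF obtained with ASL MRI is the primary MR outcome in this pilot", but gives no reader and no masking for this trial's scans. Its one statement on blinding concerns the completed six-subject feasibility work, in which an investigator at UCLA "performed CBF analyses and readings blinded to pre- and post-RLIC treatment". Section 11 is headed "RANDOMIZATION, BLINDING, AND DATA MANAGEMENT", but its text covers only allocation and data handling. Under Protection Against Risk, Section 13 adds that "All neuroimaging and biomarker data will be de-identified".

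**The concern.** Section 12 appears to describe a control arm that the trial does not have. A reader who saw only that section could take the comparison as sham-controlled.

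The second worry follows from the first. With no sham during the 30 treatment days, participants and site staff know the assignment, so protection against biased measurement has to come from the people who read the outcome. The protocol writes that protection down for the biomarkers but not for CBF, its leading imaging measure. Aim 2 compares CBF change between arms, and the results are meant to help plan the next trial. A reading bias in one arm would move the estimated difference, and the confidence interval would give no sign of it.

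**Working it through.** **1. The plan's own figures.** Inputs from Section 12: five subjects per arm, 90% two-sided intervals, SD 1 or 8, mean changes of 10% and 0%.

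- One-group mean: t(0.95, 4 df)/√5 = 2.132/2.236 = 0.953 for SD 1, and 8 × 0.9534 = 7.63 for SD 8. The plan states ±0.95 and ±7.63.
- Difference between arms: SE = 8 × √(1/5 + 1/5) = 5.06. Half-width = t(0.95, 8 df) × SE = 1.860 × 5.06 = 9.41. Interval = 10 ± 9.41 = (0.59, 19.41). The plan states ±9.4 and (0.6, 19.4).

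All reproduce to rounding.

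**2. Effect of the label.** The half-width uses only the SD and the number per arm. With AMM alone as the control at the same 0% change, the interval is still (0.6, 19.4). If one assumed a nonzero change on AMM alone (the documents give no figure), the interval would move at the same width: 2% gives 8 ± 9.41 = (-1.4, 17.4), and 5% gives 5 ± 9.41 = (-4.4, 14.4). That would be a different hypothetical, not a correction of this one.

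The single five-minute test inflation in Section 5 does not make the control a sham arm. Every subject has it before randomization, and Section 3 places the baseline scan 3-5 days after randomization so that any effect washes out.

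**3. What a reader must know to bias the result.** The estimate is the mean change on RLIC minus the mean change on control. Write B and F for a subject's baseline and close-out CBF.

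- *Knows scan order only.* Adding c to every close-out reading adds c to the change in both arms: (R + c) − (C + c) = R − C. On the percent scale, inflating every close-out value by a factor (1 + c) multiplies the difference by (1 + c). A true difference of zero stays zero.
- *Knows arm only.* The reader shifts both of a subject's scans. An additive shift cancels in F − B. A proportional shift k cancels in percent change: (kF − kB)/kB = (F − B)/B. An additive shift a on the percent scale rescales the change by B/(B + a) and does not create a change where there is none.
- *Knows both.* The reader can add b to the change in one arm, and the difference moves by b.

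A directional shift therefore generally needs both pieces of information.

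**4. Size in that last case.** The documents give no value for b, so these are assumed values. Coverage of the nominal 90% interval is P(|T| < 1.860), with T noncentral t on 8 df and noncentrality b/5.06.

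| b (points) | Noncentrality | Coverage | Illustrated interval becomes |
|---|---|---|---|
| 2 | 0.395 | 87.8% | (2.6, 21.4) |
| 4 | 0.791 | 81.2% | (4.6, 23.4) |
| 8 | 1.581 | 57.8% | (8.6, 27.4) |

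The arithmetic holds for any one-arm shift of that size from any source. It does not show that such a shift is likely here. The largest value equals the illustrated SD and is 8/10 = 80% of the illustrated effect.

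**The case for a change.** The strongest opposing case is that the authors write masking down when they intend it, as Section 8 shows, so its absence from Sections 9 and 11 is telling. De-identification is listed as a safeguard for confidentiality, and a de-identified scan can still carry its date or arm. The feasibility study had no control arm, so its blinding could not have covered assignment. Although ASL output is quantitative, Section 9 itself speaks of readings and reports results by territory and side, which leaves room for judgement.

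Part of this stands. The available text does not commit the trial to masked CBF reading, and de-identification alone is not masking. The sentence on de-identification also points to a Sources of Material section that is neither in the available text nor in the table of contents, so the details of image handling cannot be checked. Figure 1 and some text between Sections 5 and 6 are not available either, but Sections 9 and 11, where such a statement would belong, are.

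The step from silence to unprotected does not stand. No sentence has scans read by someone who knows the arm. Section 9 presents the feasibility work as a test of the ASL protocol planned for this trial, and there de-identified scans went to UCLA and were read blind to order. Carrying that practice over, even without masking of assignment, would block most of the route to bias in step 3.

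**Conclusion.** The concern does not call for a change. The word sham in Section 12 is a clerical slip in an illustrative sentence. Sections 3 and 10 leave no doubt about the control arm, and ±9.4 and (0.6, 19.4) are correct for RLIC against AMM alone on the stated assumptions. The design, sample size, estimates and planned analyses are the same whichever word is used.

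The missing statement on CBF reading is a gap that the imaging team can be expected to fill sensibly, given de-identified images, its own earlier blinded reading of the same ASL protocol, and the masking already written for the biomarkers. This conclusion assumes that at least scan order is masked when this trial's scans are read. It would change if a document showed CBF being read by someone who knew both the arm and the order of the scans. The coverage figures of 87.8%, 81.2% and 57.8% apply only in that case and only for assumed shifts, so they give no measure of a defect in the plan.

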## **13. PROTECTION OF HUMAN SUBJECTS**

**Risks to the Subjects:** The risks of the Doctormate device might include discomfort, numbness or tingling in the hands and arms when the device is inflated, and a warm feeling when it is deflated. The device may also cause bruising in the arm or petechiae. There is also the theoretical possibility of a small risk of a venous clot

forming in the arm. However, in our review of the literature we have not found any reports of blood clot formation with RLIC and there were no instances of venous thrombosis or any serious adverse event in either of the two published trials in China. In one of those trials, 30 subjects over age 80 used the Doctormate device twice per day on both arms for 6 months and the following risks were noted in that trial: "Transient sporadic petechiae were observed in 3 cases during the first 30 days of the study, but disappeared soon after without discontinuing treatment. No ecchymosis, tenderness to palpation, edema, skin breakage, or other skin lesions were observed. No deep vein thromboses were detected by vascular sonography during or at the end of the 180 days of treatment". In our pilot trial, we will only be using the device once per day for a period of 30 days, which is a considerably lower dose than previously used in the two Chinese trials. In both animal and human experiments for cardiac or brain conditioning, there are no examples where RLIC increased CBF above normal levels or resulted in intracerebral hemorrhage.

## **Risk Analysis and Risk Mitigation**

All SAEs and any deaths will be reported to the Institutional Review Board within 24 hours.

The risks related to participation in this trial are related to the a) RLIC device; b) MRI scan; c) phlebotomy; d.) medications associated with AMM; and e) loss of confidentiality.

a.) Device related. Although we don't anticipate any serious adverse events related to the RLIC device based on experience with the same device in two Chinese trials, patient safety is of paramount importance in this trial and there are operations in place for monitoring adverse events (see Protection Against Risk below). The risks that are possibly anticipated with the RLIC device include:

- Petechiae on the arm
- Skin rash or hypersensitivity to the cuff
- Thrombosis of veins in arm
- Swelling of the arm
- Pain and discomfort in the arm
- Muscle or nerve injury in the arm

b.) The risks that are associate with MRI include

- Claustrophobia and anxiety from the MRI

c.) The risks associated with phlebotomy are

- Discomfort or bruising of an arm from venipuncture required for biomarkers and routine blood tests

d.) All of the medications used in this study (aspirin and clopidogrel and the medications to control risk factors) have been approved by the Food and Drug Administration (FDA) for the conditions for which they will be prescribed in this study and are not investigational. The major side effects of aspirin are major hemorrhage and peptic ulceration. Other possible side effects of aspirin include heartburn, ringing in the ears, nausea and vomiting. The most common side effects of clopidogrel are skin rash, bruising, itching, nausea, vomiting, diarrhea, intestinal discomfort. A less common but more serious side effect of clopidogrel is major gastrointestinal or brain hemorrhage. The most serious side effect of clopidogrel is a clotting disorder called thrombotic thrombocytopenic purpura (TTP) but this is very rare (1 in 15,000-20,000 treated subjects). The combination of clopidogrel and aspirin is commonly used for 90 days after stroke or TIA in patients with intracranial stenosis following the SAMMPRIS trial and will be prescribed for the duration that subjects participate in this pilot study (33-35 days). The combination of aspirin and clopidogrel is associated with a significantly higher risk of major bleeding compared with clopidogrel or aspirin alone. The risks associated with statin therapy are a persistent increase in liver enzymes (0.0 - 0.4%), myalgia (2.8%), muscle weakness with increase in CK levels > 10 x upper limit of normal (0.03 - 0.1%), and rarely rhabdomyolysis that can potentially lead to renal failure. The risks associated with antihypertensive medications include hypotension, dizziness, headaches, weakness,

allergic reactions, diarrhea, hypokalemia or hyperkalemia depending on the type of blood pressure medication taken, cough (with ACE inhibitors), and angioedema (ACE inhibitors).

e.) There is the risk of loss of confidentiality

The principles of Informed Consent, according to FDA Regulations and ICH guidelines on GCP, will be followed. All subjects must provide informed consent to participate and only the participant can provide informed consent, which must be cosigned by a study investigator. Once a subject's eligibility has been confirmed by the site investigators, the subject will be approached to participate in the trial. The consent form includes a section describing a screening process whereby the subject will receive one session of RLIC treatment lasting 5 minutes to ensure that the subject can tolerate the treatment. Subjects who cannot tolerate the treatment will be called by the study coordinator at 1 week but will not participate further in the trial. Only subjects who can tolerate the screening treatment will be randomized to one of the treatment arms.

### **Protection Against Risk**

The research coordinator will call subjects randomized to the RLIC group weekly and will use a standardized questionnaire to ask subjects about adverse events (see Appendix 1). For the pain question, we will utilize a visual analog pain scale of 0 to 10 and provide this to the subjects randomized to the RLIC group. At the weekly phone call, the research coordinator will ask the degree of pain using this scale. If the score is > 2, the site investigator will be notified and will contact the subject by phone to review the level of discomfort. Additionally, If the subject answers "yes" to any other questions, we will ask the subject to come in to be examined. If we suspect a venous thrombosis because of swelling or pain, we will perform a venous ultrasound to rule out a deep venous thrombosis. We will also obtain the phone number of a relative or friend in order to reach the subject if we have trouble reaching the subject. All subjects will be given the telephone numbers of the principal site neurologist and site coordinator to report any clinical events or to ask questions about the study.

Subjects who are claustrophobic will not be enrolled in this study. To reduce the risk of phlebotomy, only trained phlebotomists will perform venipuncture. All neuroimaging and biomarker data will be de-identified as stated under "Sources of Material". Copies of the source documents used to collect data for study subjects will be kept in confidential binders at the participating sites. All these measures will ensure against loss of confidentiality.

Side effects of any medications prescribed to subjects as part of routine care of subjects with intracranial stenosis will also be monitored. These side effects will be minimized by recommending use of enteric-coated aspirin, checking liver enzymes and CK for subjects on a statin if clinically indicated, and instituting appropriate treatment should side effects arise.

**Potential Benefits of the Proposed Research to the Subjects and Others.** Subjects enrolled in this study may benefit from the increased medical supervision that occurs by participating in this study; however, no benefit from this supervision or the RLIC treatment can be guaranteed. If RLIC is indeed effective as suggested in the previous Chinese trials, the subjects randomized to RLIC may have a reduction in stroke. Based on previous human studies, there are minimal risks to RLIC and there is the potential that this treatment could ultimately be shown to be effective for lowering the risk of stroke in patients with ICAS, one of the highest risk stroke-prone conditions.

**Importance of the Knowledge to be Gained.** The risk of recurrent stroke in patients with ICAS is very high, about 20% at one year even with aggressive medical management (AMM). RLIC has the potential to reduce this risk of stroke and avoid disability for patients with ICAS based on the preliminary trials performed in China. Since the anticipated risks of RLIC are low, these risks are reasonable in relation to the importance of the knowledge that will be gained from this study. This study will provide key pilot data to evaluate the tolerability and adherence to RLIC and will enable calculation of the sample size for a subsequent larger NIH-funded

multicenter Phase I / II trial that will provide more rigorous data on the mechanisms of action of RLIC and the potential efficacy of RLIC in preventing stroke in these subjects. If these two goals are achieved in the Phase I / II trial, we will submit another grant to NIH to fund a definitive large multicenter Phase III trial to establish the efficacy of RLIC for subjects with ICAS. If that planned trial is positive for RLIC, it will lead to a new treatment for this common and high-risk disease and will provide a strong rationale to test RLIC for related conditions such as patients with extracranial carotid stenosis and patients with vascular cognitive impairment

**Safety Monitoring.** [name] MD, Professor of Neurology at the Medical College of Georgia, will serve as the Safety Officer. [name] has over 30 years of experience as a vascular neurologist, is Board Certified in Internal Medicine and Neurology, and served as the Safety Officer for a past trial of minocycline in acute ischemic stroke conducted at the Medical College of Georgia, and two other sites. All adverse events (AE) and serious adverse events (SAEs) will be reported to [name] and the site's IRB within 24 hours. A SAE is defined by any medical experience regardless of its relationship to the investigational device or study drugs that occurs during subject enrollment in this trial that results in any of the following: (1) inpatient hospitalization or prolongation of a hospitalization; (b) persistent or significant disability/incapacity; (c) death of the study subject, or (d) necessitates an intervention to prevent a permanent impairment of a body function or permanent damage to a body structure. [name] will make a determination of whether an AE or SAE in any way is related to the Doctormate device.

Stopping rules: If the Safety Officer determines that an SAE is definitely related to the device, the study will be stopped and a review will be conducted by the safety monitor of the outcomes of all enrolled subjects, who will determine whether enrollment in the study can be restarted. Since there are only 10 subjects that will be enrolled in this pilot study, this decision to restart enrollment cannot be based on a formal statistical stopping rule. Instead it will be based on a clinical impression of likely harm to subjects from continuing ischemic conditioning, which the evidence from much larger completed trials of ischemic conditioning in subjects with coronary and intracranial occlusive disease suggests is very unlikely.

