Moreover, in terms of acute cardioprotection, pre-clinical studies have shown that 4 to 6 cycles of 5-minute durations appear optimal. Using 4 cycles instead of 5 cycles (the regimen used in the Chinese trials) will lessen the total duration of each treatment from 45 minutes to 35 minutes, which we expect will increase adherence. We chose to measure changes in CBF and biomarkers at 30 days for this pilot study because some preliminary human studies by the MCG group show that CBF increases within 6-24 hours of first use of RLIC, and a preclinical study (in a mouse model) shows that the increased CBF after RLIC is sustained to 28 days with daily RLIC treatment. Moreover, the first 30 days after enrollment in SAMMPRIS was the highest risk period for recurrent stroke so it is important to determine if the CBF and biomarker responses to RLIC persist for this period.

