
Subject Study Number \_\_\_\_\_

End of Week (Circle one) 1.\_\_\_\_\_, 2.\_\_\_\_\_, 3.\_\_\_\_\_, 4. (close-out visit) \_\_\_\_\_

Date\_\_\_\_\_

1.) Have you experienced any swelling in either of your arms? (Y/N)

*Coordinator Comment: (if yes, specify which arm(s) and where in the arm(s), i.e., above, at or below cuff)*

2.) Have you had any discoloration (change in color) in either of your arms after any treatment? (Y/N)

This could be redness, blueness, small red dots, red or purple blotches in your arm

*Coordinator Comment: (if yes, specify which arm(s), where in the arm(s), and type of discoloration)*

3.) Have you had any persistent tingling or numbness in either of your arms? (Y/N)

*Coordinator Comment: (if yes, specify which arm(s) and where in the arm(s))*

4.) During the cuff inflations or any time between use of the cuff, have you had pain in either arm? (Y/N)

*Coordinator Comment: if yes, ask subject to use visual analog pain scale given to subject after enrollment to rate the discomfort on the Pain scale between 0 and 10, and specify which arm(s) and where in the arm(s) is the pain located) Pain rating\_\_\_\_\_*

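### The weekly adverse-event call is meant to cover any event, but its form asks only about arm symptoms and goes only to the RLIC arm, so non-serious events are found incompletely and unequally

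*Combined protocol and SAP*

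**What the plan says.** Four places in the combined protocol and SAP bear on this.

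- **Purpose of the call.** Section 10 has the coordinator telephone every week until close-out, "to document any problems with the device or any adverse events using a questionnaire (see Appendix 1". The paragraph opens with subjects randomized to RLIC.
- **Who is called.** Section 13 (Protection Against Risk) is explicit: "The research coordinator will call subjects randomized to the RLIC group weekly and will use a standardized questionnaire to ask subjects about adverse events".
- **What is asked.** Appendix 1 begins with "Have you experienced any swelling in either of your arms? (Y/N". Its other three items are arm discoloration, persistent arm tingling or numbness, and arm pain. The last time box reads "4. (close-out visit".
- **What must be reported.** Section 13 (Safety Monitoring) sends all AEs and SAEs to the Safety Officer and the site's IRB within 24 hours, in either arm. The officer judges whether each is related to the device.

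For both arms, section 13 also provides telephone numbers for reporting clinical events and says that side effects of medications are monitored, without a schedule or form. Section 3 brings every subject back on days 33-35 and names MRI and a blood draw at that visit, but no adverse-event questions.

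**The concern.** The form is narrower than the call's stated purpose, and much narrower than the reporting duty. The 24-hour rule can act only on events that the site learns of.

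The protocol itself says why events outside the arm matter in both groups. On dual antiplatelet therapy, which all subjects take, section 13 states: "The combination of aspirin and clopidogrel is associated with a significantly higher risk of major bleeding compared with clopidogrel or aspirin alone". On timing, section 6 notes that "the first 30 days after enrollment in SAMMPRIS was the highest risk period for recurrent stroke". Even so, no item is aimed at new neurological symptoms, bleeding, an emergency visit or any other health problem.

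At stake is the completeness of the safety record for ten subjects. The Safety Officer uses that record to attribute each event and, after a stop, to review the outcomes of all enrolled subjects before enrollment can restart. That decision is a clinical impression with no statistical rule behind it, so it depends on how fully each subject's events were recorded.

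**Working it through.** The plan states no figure on this point, so the check is a comparison of passages and a count.

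**1. Content of the form.** Items about the arms: 4 of 4. The list in section 13 headed "The risks that are possibly anticipated with the RLIC device include" has six entries, and the form touches all six:
- petechiae and rash: item 2
- venous thrombosis: items 1 and 4
- swelling: item 1
- pain: item 4
- muscle or nerve injury: items 3 and 4

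The form therefore suits its device purpose. Item 3 could pick up a lasting sensory deficit in an arm, but it asks only about persistent symptoms, so it is not a TIA question.

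**2. Scheduled questionnaires, RLIC arm (n = 5).** The documents give two readings.
- *By the form's boxes:* weeks 1-3 by telephone and week 4 at close-out. Calls: 5 × 3 = 15. With close-out: 5 × 4 = 20.
- *By section 10 (every week until close-out, day 33-35):* counted from enrollment, calls fall on days 7, 14, 21 and 28. Counted from device start on day 3-5, a fourth call falls on day 31-33 (3 + 28 to 5 + 28), on or before close-out. Calls: 5 × 4 = 20, with close-out additional.

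So there are 3 or 4 calls per subject, and the two passages need to be reconciled.

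**3. Scheduled questionnaires, AMM-alone arm (n = 5).** In the available text: 0. Text at the junction of sections 5 and 6 was not available for this review and might describe contacts.

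**4. AMM-alone interval with no described contact.** Baseline tests are 3-5 days after randomization and close-out is 33-35 days after enrollment. Assuming both are counted from the same day, the interval is 33 − 5 = 28 to 35 − 3 = 32 days. This is an upper bound: the unavailable text, risk-factor management or side-effect monitoring may bring contacts that are not scheduled in what can be read.

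**5. Other prompts.** The Appendix 2 diary gives the RLIC arm 5 × 30 = 150 daily entries, with a comments column where other problems can be written. AMM-alone subjects have no diary.

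**6. What unequal detection could do (illustration only).** The documents give no rate for TIA or minor bleeding and no capture rates. Assume the same true risk p per subject in both arms, and capture of c = 90% in one arm and 50% in the other. The chance of recording at least one event among five subjects is 1 − (1 − pc)^5.

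| Assumed p | c = 90% | c = 50% |
|---|---|---|
| 5% | 21% | 12% |
| 10% | 38% | 23% |
| 20% | 63% | 41% |

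This shows the direction and possible scale of the effect. It does not estimate how many events this trial would miss.

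**The case against.** The strongest case against is that this is a ten-subject mechanistic pilot and the form does the job that the third aim in section 2 needs: tolerability of a device that only one arm takes home. That stands, and the arm items should stay with the RLIC arm.

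Several other counterpoints also stand:

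- The call's stated scope is wider than the form, so RLIC subjects can volunteer other events on the call or in the diary's comments column.
- All subjects have telephone numbers and a close-out visit, and medication side effects are said to be monitored.
- An open question will bring in minor complaints, each of which enters the 24-hour reporting route.

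Three stronger readings are tempting, and the documents do not support them:

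- *A reader might infer that a safety comparison between arms is biased.* None is planned: sections 2 and 12 concern CBF, biomarkers, and RLIC feasibility, tolerability and adherence.
- *A reader might infer that the stopping rule is compromised.* The stop is triggered by an SAE that the Safety Officer considers definitely device-related. AMM-alone subjects have no home device, and SAEs are the events most likely to surface anyway.
- *A reader might infer that AMM-alone subjects go unobserved for a month.* The 28-32 days are only an upper bound on the time without a described contact.

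What does not stand is the argument that this is mere preference. The only form named for the call does not cover the scope that section 10 gives the call.

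**Conclusion.** The point holds as a modest weakness in safety detection. Followed as written, the plan asks RLIC subjects about arm symptoms only and, in the available text, asks AMM-alone subjects nothing on a schedule. Events below the SAE threshold, such as a TIA or minor bleed without admission, will be found incompletely in both arms and less readily in the AMM-alone arm.

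The firm numbers are 4 of 4 arm items, and 3 or 4 scheduled calls per RLIC subject against none described per AMM-alone subject. No planned analysis is invalidated. Events causing hospitalization or disability would probably reach the site by existing routes. The consequence is a thinner concurrent background for the Safety Officer's attribution of events and review before a restart.

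The AMM-alone half assumes that the unavailable text schedules no such questioning for that arm. The gap in the form's content does not depend on that assumption. This should be changed because it is cheap, but it is not a reason to hold the trial.

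**What to change.** 1. Add a short general section to Appendix 1: new stroke or TIA symptoms, bleeding, hospital or emergency visit, and any other health problem. Ask it of both arms on the same weekly schedule and at close-out. If AMM-alone contacts are already planned, attach it to those.
2. Keep the four arm items for the RLIC arm only and report them separately as device tolerability.
3. Reconcile section 10, where calls continue weekly until close-out on days 33-35, with the form's last box, "4. (close-out visit", so that the number of calls is fixed.
4. Section 13 says of a positive answer "to any other questions, we will ask the subject to come in to be examined", with pain handled separately. The sponsor should state whether that sentence applies to the added items.

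**Cost.** Added AMM-alone calls: 5 × 3 = 15 to 5 × 4 = 20, fewer if contacts already exist. The form becomes longer on the existing 15 to 20 RLIC calls, and five AMM-alone close-out visits gain a short questionnaire. Some added follow-up is likely, and more minor events will enter the 24-hour route to the Safety Officer and IRB; the documents give no rate from which to count either. The RLIC-only diary would still leave some unequal prompting, which the report should acknowledge.
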